5 POPULATION

5.1 Participant Inclusion Criteria

To be eligible to participate in this study, an individual must meet all of the following criteria:

- Willing and able to provide signed and dated written informed consent
- Willing to comply with all study procedures and be available for the duration of the study
- Male or female, aged 18 or older
- Patients who clinically meet clinical criteria for SOC scope examination of the upper aerodigestive tract. This includes signs and symptoms such as dysphagia, nasal obstruction, neck mass, throat pain, and hoarseness.

5.2 Participant Exclusion Criteria

An individual who meets any of the following criteria at baseline will be excluded from participation in this study:

- Withdrawal of consent during the study duration
- Subjects who have complications from the SOC exam
- Anyone unable to undergo the SOC exam

5.3 Strategies for Recruitment and Retention

Optimization Phase: Based on our prior work, 20 patients are seen daily per provider within the HNC Clinic at Duke University. We have 2 full time surgeons and 2 part time surgeons that see patients. About 50% of these patients require a SOC scope procedure. It is estimated that up to 50% of these patients would be willing to participate in this study. Thus, our target of having up to 50 subjects to assess each scope prototype version in order to make improvements focused on the stated outcomes is feasible and can be accomplished within 2-3 weeks. Participating HNC providers will be trained on the study and use of device prior to start of subject recruitment.

Potential subjects will be identified by their HNC provider during a SOC visit. The provider will ascertain interest in study participation. If a potential subject expresses interest then a member of the study team will review eligibility and conduct the consent process prior to the SOC scope exam and start of study activities. If the subject is not able to tolerate or has complications from the SOC scope exam then he/she will be considered a screen failure.

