4 STUDY DESIGN

The Optimization Phase (Phase 1) Due to new regulatory restrictions in Vietnam, the optimization phase for Aim 1 will now be conducted at Duke University. This will allow us to obtain data from subjects and providers that will be helpful in determining if additional adjustments or improvements are needed to the FNS prototype. Direct comparison between the current approach using available SOC flexible scopes with the new approach using the low cost FNS will be made. Potential eligible subjects being seen in the Duke Head and Neck Surgery and Communication Sciences clinic meeting clinical indication for a SOC scope exam will be approached for the study. If consent is given, the subject will first undergo the “SOC” scope endoscopy. Then the FNS exam will be performed using the prototype. A post-procedure survey will then be administered and completed by both the provider and subject. Post-procedure data will be collected in three areas: technical assessment, physician feedback, and subject feedback.

The entire study procedure after consent takes about 5 minutes: ~one minute for the SOC scope procedure, ~one minute to change to the FNS scope, ~one minute for the FNS procedure, ~one minute to complete the study survey. We will have at least two low cost FNS to use. To allow for high level disinfection (HLD) between use, we will recruit 2 study participants in the morning clinic session, and 2 in the afternoon for a total of 4 participants per day.

Data will be collected using REDCap on a tablet to enable real time data collection. REDCap is a browser-based survey data collection platform. The data input tablet will be password protected and coded. Data will be stored in the REDCap database. Data will be collected after each FNS scope procedure and will include a technical assessment from the physician. This assessment includes ease of use, and quality of the image. Finally, the subjects will use a numeric scale to assess and compare pain experience between the two scope procedures. Collection of adverse events will also be via REDCap at this time.

The study participation is completed on the scope when survey information is collected. Data collection for each FNS prototype will involve a cohort of up to 50 subjects.

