14 QUALITY CONTROL AND QUALITY ASSURANCE

PHI will be collected and stored on subjects enrolled at Duke. All potential subjects who are approached about study participation will be entered in a screening log. Those who agree to participate by providing written informed consent will be entered in the enrollment log and assigned a unique study ID number. Identifiers such as name, medical record number and date of study visit will be included in the enrollment log and the REDCap database. If electronic consent is obtained then email address will also be collected. Quality reviews will be done by the PI and study team on a weekly basis, and per the independent internal monitor as outlined in the CQMP. The PI and Study Coordinator (SC) will be responsible for correcting procedures that are not in compliance with protocol and quality control issues (correcting errors in data entry).

A kick-off meeting will be conducted to train study staff on the protocol and use of FNS device prior to start of study activities.

The Industry partner will assess the quality of the scopes prior and during usage. The industry partner will provide adequate support for repair or replacement as needed.

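### The provider who puts patients forward also rates the FNS, and no rule fills the four daily slots, so selection of easier exams is possible and would leave no record

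*Combined protocol and SAP*

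**What the plan says.** - **Who selects.** Section 5.3: "Potential subjects will be identified by their HNC provider during a SOC visit". The Recruitment paragraph of the Protocol Summary likewise has the treating physician make the first approach. A study team member then checks eligibility and takes consent, but only for patients already put forward.
- **Who rates.** The survey in the Supplemental Materials is completed by the clinician who did the exam. It holds the ease-of-use item and the video ratings of both scopes. Section 12.3 confirms that physicians report the primary outcome. The subject answers the pain item.
- **Blinding.** None is possible as designed. Sections 4 and 7.1 fix the order as SOC scope first, FNS second.
- **Slots.** Section 4, because of disinfection time: "we will recruit 2 study participants in the morning clinic session, and 2 in the afternoon for a total of 4 participants per day".
- **Supply.** Section 5.3 puts the daily load at 20 per provider, names two full-time and two part-time surgeons, and takes roughly half of the patients to need a SOC scope exam. On willingness it says: "It is estimated that up to 50% of these patients would be willing to participate in this study".
- **Record.** Section 14: "All potential subjects who are approached about study participation will be entered in a screening log".
- **Decision rule.** Section 12.3 requires 90% favourable responses on each of three outcomes at 37 subjects. If the rates fall between 50% and 90%, recruitment continues and the same test is applied at 50.

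The text contains no consecutive, random or first-eligible rule for filling the slots.

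**The concern.** Discretion over who is enrolled lies with the person whose unblinded rating decides two of the three success criteria, including the primary. Supply above the daily cap gives room to use that discretion, consciously or not. A provider who expects a difficult exam can simply leave the patient unapproached, and that patient then appears nowhere in the study records. Neither the monitors nor the DSMB could reconstruct afterwards how the enrolled subjects compare with all patients who needed a scope exam.

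At stake is what the 90% rate describes. The stated population is adults who meet clinical criteria for a SOC scope exam. If the harder exams are under-represented, and if the prototype falls behind the SOC scope mainly in those, the phase could be declared a success without having seen the failures that an optimization study is meant to find.

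**Working it through.** **1. The plan's accrual figure.** Section 5.3 says that enrolling up to 50 subjects per prototype "is feasible and can be accomplished within 2-3 weeks". At 4 a day, 50 / 4 = 12.5 clinic days, and 12.5 / 5 = 2.5 five-day weeks. The figure reproduces, so the cap of 4 a day, not the supply of patients, fits the stated timeline.

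**2. Supply against slots.** Willing patients per provider per day = 20 × 50% × (up to 50%) = up to 5.
- Two full-time surgeons: up to 2 × 5 = 10 a day, or 10 / 4 = 2.5 candidates per slot.
- All four surgeons in clinic: up to 20 a day, or 5 per slot. The part-time fraction is not given, so this is the upper end.

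The 50% willingness is a ceiling. For the two full-time surgeons (20 scope patients a day):

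| Willingness | Willing patients a day | Slots |
|---|---|---|
| 50% | 10 | 4 |
| 40% | 8 | 4 |
| 30% | 6 | 4 |
| 20% | 4 | 4 |

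With two surgeons, a surplus exists at any willingness above 4 / 20 = 20%.

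**3. Is the selector the rater?** No single sentence says so. It follows from three places read together: the treating physician approaches (Protocol Summary), the patient's own provider identifies (5.3), and the clinician who performed the exam completes the survey (Supplemental Materials).

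**4. Illustration of size.** The true rate and the degree of selection below are assumptions; nothing in the documents supplies them.
- Thresholds: 0.9 × 37 = 33.3, so 34 of 37; 0.9 × 50 = 45 of 50; 0.5 × 37 = 18.5, so 19 to 33 of 37 leads to continuation.
- Chance of meeting one criterion = P(X37 ≥ 34) + P(19 ≤ X37 ≤ 33 and X50 ≥ 45), binomial with rate p.
- If a share k of would-be poor scorers is not approached, the enrolled rate is p′ = p / [p + (1 − p)(1 − k)].

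With p = 0.85:

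| k | Enrolled rate p′ | Candidates removed, 0.15k | Chance of meeting the criterion |
|---|---|---|---|
| 0 | 0.850 | 0% | 26% |
| 10% | 0.863 | 1.5% | 34% |
| 25% | 0.883 | 3.75% | 50% |
| 50% | 0.919 | 7.5% | 81% |

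Even the last row removes only 7.5% of candidates, whereas 4 slots for 10 willing patients leaves 60% out. The table covers one criterion; success needs all three.

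**The case against.** The strongest objection is the within-subject design. Ease of use and pain are both asked as comparisons of the second scope with the first, in the same patient minutes apart. A nose that is hard for both scopes can still score as the same. This stands: selection inflates the rate only if the FNS does relatively worse than the SOC scope in difficult patients. It does not dispose of the point, because pairing cannot remove an extra difficulty specific to the prototype.

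Other objections also limit the claim:
- A reader might take 10 willing patients a day as a minimum. Section 5.3 gives willingness as an upper limit, so 10 is the most that the two full-time surgeons supply.
- A reader might take section 2.2 as showing that scope diameter is a known problem with the study device. That feedback concerned the earlier basic prototype, and the section says the changes are being built into the one tested here.
- A reader might expect consecutive approach to bring patients with nasal obstruction into the 90% rate. Section 5.2 excludes anyone who cannot undergo the SOC exam, and 5.4 allows patients in whom the FNS cannot be passed to be withdrawn and replaced. That is a separate issue, and approach order does not settle it.
- The subject rates pain, and the documents give no particular reason why the video rating should depend on which patients are chosen.
- This is a single-site prototype study, and provider-identified convenience sampling is a design choice, not a contradiction in the plan. That is fair, but the choice is cheap to improve.

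**Conclusion.** The concern holds as an open route to selection bias, not as a demonstrated bias. The selector and the rater are the same person on a joint reading of the documents, candidates exceed slots at any willingness above 20% with two surgeons, no rule fills the slots, and patients passed over are not logged. Inflation of the 90% rate further requires that the FNS be relatively worse in difficult patients, and the documents do not say whether it is.

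The size cannot be derived from the documents. The rise from 26% to between 34% and 81% on one criterion rests on an assumed true rate of 85% and on assumed degrees of selection. A reader might go further and suppose that selection lifts the enrolled rate from 85% to 95%, which would take the chance from 26% to 97%. That would require about 70% of would-be poor scorers to be passed over, since 0.85 / (0.85 + 0.15 × 0.30) ≈ 0.95. Providers would have to recognise them before either scope is used, because consent precedes the SOC exam. The documents do not support so strong a shift. Nor do they support an inference that providers will select in this way.

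**What to change.** - **Sections 4 and 5.3:** state that in each morning and afternoon session, patients found to need a SOC scope exam are approached consecutively, in the order seen, until two have consented.
- **Section 14:** extend the screening log to every eligible scope patient up to the second enrolment of the session, with the reason for anyone not approached.

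The cost is a sentence or two in each place, a few more log lines per session and slightly less scheduling freedom. With up to four surgeons sharing the slots, someone must keep track of the order across rooms. Patients seen early in a session will be somewhat over-represented. The observed success rate may be lower. Accrual should hold as long as willingness stays above the 20% break-even for two surgeons.

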5.4 Participant Withdrawal or Discontinuation from Study Procedures/Intervention

5.4.1 *Reasons for Participant Withdrawal or Discontinuation from Study Procedures/Intervention*

Subjects are free to withdraw from participation in the study at any time upon request.

An investigator may discontinue an individual's participation in an intervention or withdraw an individual from the study if:

- The participant meets an exclusion criterion (either newly developed or not previously recognized) that precludes further study participation.
- Inability to complete the FNS exam (i.e., bilateral nasal obstruction preventing passing of the flexible FNS)

5.4.2 *Handling of Participant Withdrawals from Study or Participant Discontinuation of Study Intervention*

The reason for withdrawal will be solicited from the subject if they choose to stop the investigational scope exam and this will be recorded in the REDCap database.

Replacement participants will be recruited until enrollment is complete. Data that is already collected will be included in the analysis and not destroyed.

5.5 Premature Termination or Suspension of Study

This study may be suspended or prematurely terminated if there is sufficient reasonable cause. Written notification, documenting the reason for study suspension or termination, will be provided by the suspending or terminating party to the investigator, funding agency (NIDCR), and regulatory authorities. The principal investigator will also promptly inform the IRB and NIDCR and will provide the reason(s) for the termination or suspension.

Circumstances that may warrant termination include, but are not limited to:

- Determination of unexpected, significant, or unacceptable risk to participants.
- Insufficient adherence to protocol requirements.
- Data that are not sufficiently complete and/or evaluable.
- Determination of futility.

6 STUDY INTERVENTION

6.1 Study Procedural Intervention(s) Description

A low-cost, mobile, FNS that could be used in low-resource settings was designed in 2011 by the PI and collaborators. The FNS is used for assessment of the entire upper aerodigestive tract by Ear, Nose, and Throat (ENT) doctors or otolaryngologists and is part of SOC in developed countries. This scope is inserted through the nasal passages into the pharynx, enabling a full view of all areas at risk for HNC.

This study will test a low cost FNS prototype based on one used in preliminary work (Figure 4). It has a self-contained monitor as well as replaceable batteries. There is an LED light in the articulating tip.

The new prototype will be built by Vivo Surgical and addresses many of the barriers to the implementation of the technology, and in consideration of aspects identified by physicians as being of particular importance. All modified and updated prototypes will be submitted to the IRB at Duke, Approval for use will be required prior to any clinical use.

Figure 4: FNS prototype with LED lighted articulating tip and attached user monitor.

The protective sheath covering developed under the supplemental grant will be used once it is ready for use (refer to separate COVID19 sheath sub-study document).

6.2 Administration of Procedural Intervention

The FNS will be used only by medical providers in Head and Neck Surgery at Duke. This procedural intervention will be only administered during a clinic visit. The participation is considered complete once the subject leaves the clinic visit. The actual duration of the FNS procedural intervention is estimated to last about 1 minute.

6.3 Procedures for Training of Clinicians on Procedural Intervention

Training will occur prior to the recruitment of subjects and initiation of study activities. Training sessions, led by the PI – [name] will include details on the operation, cleaning, and care of the scopes. The clinicians for the optimization phase are faculty and are familiar with using a flexible scope.

6.4 Assessment of Clinician and/or Participant Compliance with Study Procedural Intervention

The 9 steps of the intervention FNS protocol are below.

1. Confirm understanding of procedure and subject consent. Confirm newly disinfected scope is being used.
2. Lubricate the FNS tip with gel and wipe FNS tip as needed to obtain clear image. Check mobility of FNS tip.
3. Place scope into nares with direct vision then look at screen.
4. Insert through nasal cavity being careful not to apply pressure on the nasal septum.
5. Assess nasal cavity, nasopharynx. Document any clinical findings per routine care practices.
6. Direct tip to make bend at nasopharynx and have subject breathe through the nose. This relaxes soft palate and opens airway.
7. Assess oropharynx by having subject protrude tongue. Assess larynx and hypopharynx by having subject phonate and sniff and swallow. Document and clinical findings per routine care practices.
8. Straighten tip and withdraw scope.
9. Immediately send scope for HLD per SOP. Complete study survey questions and assessment of SAE.

7 STUDY SCHEDULE

7.1 Enrollment/Baseline

- Obtain and document consent from participant on study consent form.
- Verify inclusion/exclusion criteria.
- Administer the SOC scope then FNS study intervention.
- Administer post procedural surveys:
 - Provider survey
 - Subject survey

8 STUDY PROCEDURES/EVALUATIONS

8.1 Study Procedures/Evaluations

The Study procedure includes the following:

AIM 1: FNS scope procedure

Post procedure survey

The FNS procedure has been described in section 6.4.

All surveys will be recorded via REDCap. This will be immediately completed by a study investigator and also the subject (as indicated).

(Surveys can be found under supplemental materials section of the protocol)

9 ASSESSMENT OF SAFETY

This study involves optimization of a low cost FNS. This is considered a nonsignificant risk investigational device by the FDA (21 CFR 874.4760 - Class II device). The risks are rare and include: stiff neck, sore throat, temporary loss of voice, temporary perceived difficulty breathing, bleeding, and minor damage to the lining of the airway. These are all self-limiting.

Prior to use in subjects, all study investigators will demonstrate competency in the FNS exam and study procedures. Only certified ENT surgeons listed as key personnel with the IRB will be performing the FNS exam. Manual HLD will be performed with Revital-Ox RESET, a 2% Accelerated Hydrogen Peroxide solution, per manufacture instructions for use

After each study FNS procedure, the study investigator will record any observed adverse events. If there are adverse events, the subject will be observed until stabilization of the event has occurred. These are recorded real time to the REDCap database. If there are AE or unanticipated problems (UPs), the PI ([name]) will be notified via email.

The optimization phase of this study will be conducted at Duke University Medical Center and will require safety monitoring and oversight. The Duke study team will review safety information in real time as data are collected, as well as a monthly basis. Adverse events will be reported as outlined in the sections below.

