Objectives:	
Optimize the low cost FNS by comparing to SOC scopes at Duke University Medical Center
 
We will compare the use and reliability of the FNS scope to SOC scopes available at Duke University Medical Center. This will include image quality to see structures, lighting, and steering mechanism. Key objectives include ease of use, image quality, and perceived pain. The technical and subjective feedback will optimize the device to gain efficiencies and improve tolerability. Success is considered to be that the FNS is overall non-inferior to the current SOC scopes.
 
The expected outcome is to have an optimized FNS scope for production and widespread implementation and use

Population:	Up to 50 subjects 18 years or older who meet clinical criteria to undergo a SOC endoscopic exam
Phase or Stage:	N/A
Number of Sites:	1 site
Description of Intervention:	The FNS is used for assessment of the entire upper aerodigestive tract by Ear, Nose, and Throat (ENT) doctors or otolaryngologists and is part of SOC in the USA. This scope is inserted through the nasal passages into the pharynx, enabling a full view of all areas at risk for Head and Neck Cancer (HNC). Study participation ends once the post intervention survey is completed.
Study Duration:	3 months
Subject Participation Duration:	About 30 minutes
Estimated Time to Complete Enrollment:	2 months

Recruitment: Adult subjects that will undergo SOC endoscopy at the Head and Neck Surgery and Communication Sciences clinic at Duke will be approached by their treating physician if they would be interested in participating in this study. If they are interested, the study team will approach them to review the written consent form. Once signed, the SOC procedure will take place followed by the study scope procedure. The physician will complete their portion of the post procedure survey and assess for adverse effects. The subject will complete a single question on the survey focused on comparing the pain from both procedures.

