- suggests that the research places subjects or others at a greater risk of harm (including physical, psychological, economic, or social harm) than was previously known or recognized.

9.1.2 *Adverse Events*

An adverse event is any untoward or unfavorable medical occurrence in a human subject, including any symptom temporally associated with the subject’s participation in the research, whether or not considered related to the subject’s participation in the research.

9.1.3 *Serious Adverse Events*

A serious adverse event (SAE) is one that meets one or more of the following criteria:

- Results in death
- Is life-threatening (places the subject at immediate risk of death from the event as it occurred)
- Results in inpatient hospitalization or prolongation of existing hospitalization
- Results in a persistent or significant disability or incapacity
- An important medical event that may not result in death, be life threatening, or require hospitalization may be considered an SAE when, based upon appropriate medical judgment, the event may jeopardize the subject and may require medical or surgical intervention to prevent one of the outcomes listed in this definition.

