Piker, E. G., Schulz, K., Parham, K., Vambutas, A., Witsell, D., Tucci, D., Lee, W. T. (2016). Variation in the Use of Vestibular Diagnostic Testing for Patients Presenting to Otolaryngology Clinics with Dizziness. *Otolaryngol Head Neck Surg*, 155(1), 42-47. doi:10.1177/0194599816650173

Powell, B. J., McMillen, J. C., Proctor, E. K., Carpenter, C. R., Griffey, R. T., Bunger, A. C., Glass, J. E., York, J. L. (2012). A compilation of strategies for implementing clinical innovations in health and mental health. *Med Care Res Rev*, 69(2), 123-57. doi: 10.1177/1077558711430690.

Powell, B. J., Waltz, T. J., Chinman, M. J., Damschroder, L. J., Smith J. L., Matthieu M. M., Proctor, E. K., Kirchner, J. E. (2015). A refined compilation of implementation strategies: results from the Expert Recommendations for Implementing Change (ERIC) project. *Implement Sci*, 12, 10:21. doi: 10.1186/s13012-015-0209-1.

Schroy, P. C., 3rd, Wilson, S., & Afdhal, N. (1996). Feasibility of high-volume screening sigmoidoscopy using a flexible fiberoptic endoscope and a disposable sheath system. *Am J Gastroenterol*, 91(7), 1331-1337.

Vo, Q. T., Pham, D., Choi, K. J., Nguyen, U. T., Le, L., Shanewise, T., Lee, W. T. (2017). Solar-powered hearing aids for children with impaired hearing in Vietnam: a pilot study. *Paediatr Int Child Health*, 1-6. doi:10.1080/20469047.2016.1276119

SUPPLEMENTAL MATERIALS

Post-Procedural Survey By Clinician who performed the scope exam

(Provider questions once the SOC and study FNS exams are completed):

TECHNICAL ASSESSMENT OF FNS

Were you able to complete the first scope procedure to your satisfaction?

1=no 2=somewhat 3=yes

Were you able to complete the second scope procedure to your satisfaction

1=no 2=somewhat 3=yes

Were you able to view all the structures of concern using first scope ? Y/N

If no, please explain:

Were you able to view all the structures of concern using second scope ? Y/N

If no, please explain:

Did the patient appear to have more, the same, or less discomfort with the second scope?

much more about the same much less
1 2 3

If much more: please describe why:

Were there technical issues with the second prototype scope? Y/N (if Yes, please explain below)

- _____ steering
 - _____ lighting
 - _____ video
 - _____ fogging
 - _____ image capture
 - _____ other

Ease of use: Aim 1:

Compared with the first scope, how easy was the second scope to use?

Very hard Harder same Easier Very easy

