If harder or very hard: please explain:

Quality of Images: Aim 1

Rate the video quality of the first scope: (Poor) 1 2 3 4 5 (Excellent)

Rate the video quality of the second scope: (Poor) 1 2 3 4 5 (Excellent)

Did the subject experience an AE: Y / N

If yes - please provide additional information below:

Name of adverse event: _____

Brief description of the problem or event:

Severity of adverse event (using scale below):

1. Mild: no intervention required
2. Moderate: minimal, local, or non-invasive intervention indicated
3. Severe: significant symptoms requiring invasive intervention; subject seeks medical attention

Is the adverse event related to study procedure?

1. **If related**, please specify: Possibly, Probably, or Definitely related
 - a) The event is known to occur with the study intervention, and/or
 - b) There is a temporal relationship between the intervention and event onset and/or
 - c) The event abates when the intervention is discontinued, and/or
 - d) The event reappears upon a re-challenge with the intervention.
2. **If not related**, please specify if unlikely related or Not Related)
 - a) There is no temporal relationship between the intervention and event onset, and/or
 - b) An alternate etiology has been established.

Is the problem/event unexpected? Y/N

Does the event meet the definition of a serious adverse event? Y/N

If yes, check criteria below:

A serious adverse event (SAE) is one that meets one or more of the following criteria:

1. Results in death

-
- 2. Is life-threatening (places the subject at immediate risk of death from the event as it occurred)
 - 3. Results in inpatient hospitalization or prolongation of existing hospitalization
 - 4. Results in a persistent or significant disability or incapacity

An important medical event that may not result in death, be life threatening, or require hospitalization may be considered an SAE when, based upon appropriate medical judgment, the event may jeopardize the subject and may require medical or surgical intervention to prevent one of the outcomes listed in this definition.

Outcome of adverse event: resolved or unresolved

Date of resolution:

For enrolled subjects

Pain Comparison: Aim 1-secondary objective

Did you experience more, the same, or less pain/discomfort with the second scope compared with the first scope?

much more about the same much less

1 2 3

CONSENT FORM FOR PARTICIPATING IN RESEARCH

Duke's IRB approved consent form will be provided separately

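### Section 9 asks for observed adverse events and no step asks the subject about symptoms, so mainly felt risks are likely to be captured incompletely and unevenly

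*Combined protocol and SAP*

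**What the plan says.** **How events are collected.** Section 9: "After each study FNS procedure, the study investigator will record any observed adverse events". The Recruitment paragraph of the Protocol Summary says of the clinician: "The physician will complete their portion of the post procedure survey and assess for adverse effects". Of the subject it says: "The subject will complete a single question on the survey focused on comparing the pain from both procedures". Step 9 of the procedure in Section 6.4 mentions only an assessment of SAEs.

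**The forms (Supplemental Materials).** The adverse event items sit on the "Post-Procedural Survey By Clinician who performed the scope exam" and open with "Did the subject experience an AE: Y / N". Description, severity, relatedness and seriousness follow. There is no symptom list and no prompt to question the subject. The subject's own item is "Did you experience more, the same, or less pain/discomfort with the second scope compared with the first scope", on a three-point scale.

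**What should be captured.** Section 9.1.2 defines an adverse event as "including any symptom temporally associated with the subject’s participation in the research". Section 9.2 has the PI and/or study team record every event from consent until the subject leaves the clinic. Section 9 lists the risks as "stiff neck, sore throat, temporary loss of voice, temporary perceived difficulty breathing, bleeding, and minor damage to the lining of the airway".

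**What the data feed.** The PI's weekly safety review uses the survey data (Section 12.2.1). Reports to the DSMB include event grades (Section 10). Expected events that occur more often or more intensely than anticipated go to the IRB, and Section 9.1 says that judging an unexpectedly high frequency needs appropriate data on all enrolled subjects.

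**The concern.** The definition takes in symptoms, but the collection step is worded for what the investigator observes. Three of the six listed risks (stiff neck, sore throat, perceived difficulty breathing) are mainly felt by the subject, whereas the other three can be seen or heard. If nobody has to ask, whether a felt symptom is recorded depends on the subject volunteering it or the individual clinician choosing to enquire. Capture would then be partial and would differ between clinicians.

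The weekly review, the DSMB reports and the frequency rule would inherit that gap. A report of no events could reflect how the question was asked as much as how the device performed. There is little later opportunity to correct it, because surveys are completed immediately (Section 8.1) and recording stops when the subject leaves the clinic.

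**Working it through.** **1. Is there any step that asks the subject about symptoms?**

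| Place | Who acts | What is captured |
|---|---|---|
| Section 9 | Study investigator | Observed events, after the FNS procedure |
| Protocol Summary | Physician | Adverse effects, method not stated |
| Section 6.4, step 9 | Operating clinician | SAEs |
| Clinician form | Clinician who did the exam | One yes/no, unprompted |
| Clinician form | Same clinician | How much discomfort the patient appeared to have, second scope against first |
| Subject form | Subject | Pain/discomfort, second scope against first |
| Section 9.2 | PI and/or study team | All events until departure |

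No row provides for eliciting symptoms. For discomfort the plan obtains both the clinician's impression and the subject's answer. It does not do so for the other felt risks.

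**2. The plan's own figure.** The only sample-size figure is n = 37, for a two-sided 95% interval of width 0.2 at a proportion of 0.9 (Section 12.2). A Wilson score interval gives 0.763 to 0.962, width 0.199, so it reproduces. It concerns the efficacy responses; here it supplies only the number of subjects.

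**3. Illustration of size.** The documents give no event rate and no capture fraction, so both are assumed. Let t be the true in-clinic rate of a symptom, s the share of cases recorded, and n = 37, with subjects independent.

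P(no recorded event) = (1 − t × s)^n

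| True rate t | s = 1 | s = 0.5 | s = 0.25 |
|---|---|---|---|
| 1% | 0.99^37 = 69% | 0.995^37 = 83% | 0.9975^37 = 91% |
| 5% | 0.95^37 = 15% | 0.975^37 = 39% | 0.9875^37 = 63% |
| 10% | 0.90^37 = 2% | 0.95^37 = 15% | 0.975^37 = 39% |

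**4. What a clean record would show.** With zero recorded events, the one-sided 95% upper bound on the recorded rate is 1 − 0.05^(1/n). For n = 37 this is 7.8%; for the maximum cohort of 50 it is 5.8%. Dividing by s gives the bound on the true rate. At half capture it is 7.8%/0.5 = 15.6% and 5.8%/0.5 = 11.6%.

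**The case against.** A reader might infer that the plan counts only what the surgeon sees, and that FNS event counts will therefore be biased low. The documents do not support either statement as a certainty.

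- **Symptoms are recordable.** Sections 9.1.2 and 9.2 cover symptoms and all events, the form asks what the subject experienced, and the physician is to assess for adverse effects in a patient who is still present. Nothing forbids asking, and the study team may record as well as the operator. This stands. The text shows a conflict of wording and a missing step, not a bar on recording symptoms.
- **The subject's item includes discomfort.** A sore throat or stiff neck could influence it, and the clinician form allows free text if discomfort appeared much greater. Both items are comparative, though, and neither identifies a symptom, so this answers the gap only in part.
- **The direction of error is not settled.** Subjects may arrive with throat pain or hoarseness (Section 5.1), the SOC scope always comes first (Section 4), and it carries the same felt risks (Section 2.3.1). Symptoms from either source could be counted after the FNS. This stands, and it also governs how a checklist must be worded.
- **The events are described as very rare and self-limiting.** At an assumed 1%, zero events is the likely result however subjects are asked. This stands, and is why a range of rates is shown.
- **Little depends on the counts.** No success criterion uses them, and the frequency rule has no numerical anticipated rate, so better capture alone would not make that rule operable. Both remarks are correct. The weekly review and DSMB reports still use these data.

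**Conclusion.** The concern holds in a limited form. The wording in Section 9 conflicts with Sections 9.1.2 and 9.2, and no step asks the subject about symptoms. Mainly felt risks are therefore likely to be captured incompletely and unevenly. This weakens the safety reviews and the frequency rule, which by the plan's own account needs appropriate data on all subjects.

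How much is lost cannot be derived from the documents. Under the assumed rates, halving capture matters little at 1% (69% to 83% chance of a clean record) and more at 5% (15% to 39%) or 10% (2% to 15%). These figures rest on assumed rates, a uniform capture fraction and independence between subjects. A net undercount attributable to the FNS is not shown, because presenting complaints and SOC effects could push the count the other way. The efficacy analysis and sample size are unaffected. The gap is worth closing because the remedy is small.

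**What to change.** 1. In Section 9, extend the recording instruction from observed events to observed or subject-reported events, in line with Sections 9.1.2 and 9.2.
2. Add to the subject's tablet form, before departure from the clinic, a short yes/no checklist of the six Section 9 risks plus an *other* item. Ask about symptoms that are new or worse since before the scope exams, so that presenting complaints are not counted as events.
3. Send each yes to the investigator for grading of severity and relatedness on the existing form.

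The cost is one survey revision with IRB and NIDCR approval (Section 15.2), about a minute per subject, and more mild events to grade. One limit remains: because the SOC scope always precedes the FNS, the checklist cannot fully separate the effects of the two. The current form cannot do so either.
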